5.1.4 Whole Brain Radiation Therapy

5.1.4.1 Dose Specifications

Protocol whole brain radiation therapy (WBRT) will begin on Day 8 (7 days after the start of PO IPdR administration). One treatment (fraction) of 2.5 Gy will be given daily for not more than 5 days per week (15 fractions), once daily fractionation, Monday through Friday, without any planned interruptions for a total of 37.5 Gy over 3 weeks. Therefore, WBRT will be delivered from days 8 onward (Week 2 through 4). All portals shall be treated during each treatment session. Doses are specified as the target dose, which will be the dose on the central ray at mid-separation for two opposed coaxial equally weighted beams. "Compensating beams" that minimize hot spots (these hot spots are typically present along the midline due to less tissue present in these regions compared to mid-brain) are allowed to achieve optimal dose homogeneity.

5.1.4.2 Technical Factors

Treatment will be delivered with megavoltage (MV) machines of energy ranging from 4 MV to 6 MV photons. Patients will be planned and treated using three-dimensional conformal radiation technique (3D-CRT). Field-in-field approaches to

3DCRT to optimize homogeneity are permitted. Intensity Modulated Radiotherapy (IMRT) with or without hippocampal avoidance (Fixed-gantry IMRT, helical tomotherapy or VMAT) will be allowed per institutional protocols. Partial brain cone down, stereotactic radiosurgery boost, electron therapy, particle therapy, or brachytherapy boost are not permissible during the course of the study treatment and until the DLT assessments are complete. However, patients will be eligible to undergo SRS/SRT/fractionated boosts or neurosurgery, once the DLT assessment has been completed, if felt clinically necessary.

5.1.4.3 Localization, Simulation, Immobilization and Dose prescription.

The patient will be treated in the supine position to allow planning and delivery of WBRT. A head-holding device that is transparent to x-rays must ensure adequate immobilization during therapy and ensure daily treatment reproducibility. A non-contrast treatment-planning CT scan of the entire head region extending into neck should be obtained. When using hippocampal avoidance WBRT, it is recommended the axial slice thickness should match the MRI axial slice thickness as much as possible (preferred 1.5 mm). The treatment-planning CT scan must be acquired with the patient in the same position and immobilization device as for treatment.

For 3D-CRT, the target volume will include the entire cranial contents, with flashing beyond skin and adequate margin on the skull base as visualized on the simulator or portal films to account for beam penumbra and day-to-day set-up variation. Attempts will be made to exclude the lenses and the anterior globe from the beam either by field arrangement or shielding. ‘Helmet’ portals with customized immobilization and shielding are permitted. The dose is specified as the target dose, which shall be the dose on the central x-ray at mid-separation for two opposed coaxial equally weighted beams. “Compensating beams” that block hot spots (these hot spots are typically present along midline due to less tissue present in these regions compared to mid-brain) are allowed to achieve better dose homogeneity. All portals shall be treated during each treatment session.

5.1.4.4 Hippocampal avoidance WBRT should be planned in accordance with the ongoing (or most recently completed, if no ongoing study) cooperative group protocol. The target volume will include the entire cranial contents to the foramen magnum (labeled as CTV). Care should be taken to delineate cribriform plate in the CTV. The PTV is equal to CTV without the hippocampal avoidance region. IMRT plan should be normalized such that 95% of the PTV volume receives prescription dose of 37.5 Gy (V37.5 Gy \geq 95%), D2% (Dose to hottest 2% of PTV) is \leq 40 Gy, D98% (Dose to 2% of PTV) is \geq 32.5 Gy. Variation Acceptable include, V37.5 Gy \geq 90%, D2% is \leq 43 Gy and D98% is \geq 30 Gy. QA for the physician-approved plan should be performed per institutional policies. Critical Structures

For both 3DCRT and hippocampal avoidance WBRT, the left (Lens_L) and right (Lens_R) lens should be contoured using the CT dataset only. For patients post-cataract surgery, a surrogate lens structure should be created.

For hippocampal avoidance WBRT, bilateral hippocampal contours (Hippocampi) will be manually generated on the fused planning MRI/CT image set by the treating physician according to contouring instructions specified on [http://www.rtg.org//corelab/contouringatlases/hippocampalsparing.aspx](http://www.rtog.org//corelab/contouringatlases/hippocampalsparing.aspx). Hippocampal avoidance region (Hippocampi_05) will be generated by three-dimensionally expanding the hippocampal contours by 5 mm. Bilateral hippocampal contours will be subdivided into Left (Hippo_L) and Right (Hippo_R) hippocampi. Due to variance in eye position between the CT and MRI, if possible, the left (OpticNerve_L) and right (OpticNerve_R) optic nerve should be contoured using the CT dataset only. Located above the pituitary fossa, the optic chiasm (OpticChiasm) includes both anterior and posterior limbs. It is best visualized on SPGR/MPR/TFE T1 MRI sequence, but should be confirmed on CT dataset due to potential variation in CT/MRI fusion.

OAR constraints for hippocampal avoidance WBRT are shown below:

Name of Structure	Dosimetric parameter	Per Protocol	Variation Acceptable	Notes
	D100%(Gy)	≤ 11	11 to 13	Dose to 100% of Hippocampus
	D _{max} (Gy)	≤ 16	16 to 20	Dose to hottest 0.03 cc volume of Hippocampus
OpticNerve_L	D _{max} (Gy)	≤ 37.5	37.5 to 40 Gy	Dose to hottest 0.03 cc volume of OpticNerve_L
OpticNerve_R	D _{max} (Gy)	≤ 37.5	37.5 to 40 Gy	Dose to hottest 0.03 cc volume of OpticNerve_R
OpticChiasm	D _{max} (Gy)	≤ 37.5	37.5 to 40 Gy	Dose to hottest 0.03 cc volume of OpticChiasm

In optimizing planning, the following treatment-planning priorities should be followed:

1. OpticChiasm
2. OpticNerve_L or OpticNerve_R
3. Hippocampus
4. PTV_3000
5. Lens_L or Lens_R

In the event that an OAR with higher priority than PTV cannot be constrained within Unacceptable Deviation limits, then D98% and/or V30Gy for PTV should be lowered to Variation Acceptable range to ensure that the OAR with higher priority does not exceed Unacceptable Deviation limits. Please contact the study PI (or representative) if there are challenges meeting above.

5.1.4.5 Documentation Requirements

The following documents should be submitted to the PI at the University of Maryland

- Radiation Total Dose
- Radiation Dose per Fraction
- Radiation Number of fractions
- Radiation Technique: 3D-CRT or IMRT/VMAT/Tomotherapy
- Use of Hippocampal avoidance: Yes or No
- Radiation Start Date
- Radiation Completion Date
- Treatment Interruptions/Delays
- Acute on-treatment toxicity with grades
- RT plan report with dose to organs at risk, if applicable.
- Dexamethasone pill diary during WBRT and for three weeks post-WBRT (DLT assessment period)

Copies of simulation and port films and the complete WBRT daily treatment record and calculations will be submitted to the University of Maryland, Baltimore, Department of Radiation Oncology ONLY if specifically requested.

5.1.4.6 Compliance Criteria

The planned protocol treatment should be completed without any unplanned breaks/interruptions. Dose delay/modification table has been noted in section 7.

5.1.4.7 Radiation Adverse Events

A focused history and physical examination should be performed at least once weekly during Weeks 1 through 4 (study treatment) and then towards the end of week 6 and 8 (observation period) to assess for acute treatment-related toxicity.

Acute (\leq 90 days from treatment start): Expected adverse events include hair loss, erythema of the scalp, headache, nausea and vomiting, eye/ear irritation, mucositis, taste/salivary changes, loss of appetite, fatigue, lethargy, and transient worsening of neurological deficits.

Late ($>$ 90 days from treatment start): Possible adverse events include radiation necrosis, cognitive dysfunction, visual difficulties, accelerated atherosclerosis, and radiation-induced neoplasms.

5.1.4.8 Radiation Adverse Event Reporting

See Section 8 for Adverse Event Reporting

5.2 Definition of Dose-Limiting Toxicity

Patients who are removed from protocol treatment due to non-treatment related toxicities requiring treatment delay of > 14 days are not assessable for determination of the MTD and will be replaced.

Management and dose modifications associated with the above adverse events are outlined in Section 6.

Toxicities will be recorded as adverse events on the Adverse Event case report form and must be graded using The National Cancer Institute's Common Toxicity Criteria (CTCAE) version 5.

Dose-limiting toxicity (DLT) in Parts 1 and 2 includes toxicity that is attributable to the IPdR and/or whole brain radiotherapy per the following:

- Any Grade 4+ neurologic adverse event, of any duration.
- Any Grade 3 neurologic adverse event that does not improve to baseline or Grade 1 within 7 days of onset.
- Any Grade 3 symptomatic CNS hemorrhage or ischemia
- Any Grade 4+ non-neurologic toxicity
 - An exception is Grade 4 cytopenia or metabolic abnormality without associated serious clinical symptoms (grade 4+) that improves to < Grade 4 within \leq 7 days of onset

Patients with brain metastases are likely to have other sites of symptomatic extra-cranial disease in need of palliative radiation. Hence, per standard clinical practice, patients in this study protocol will be allowed to receive palliative extra-cranial irradiation, concurrently or sequentially, as indicated. This reflects best clinical practice.

However, such a procedure, may pose a possible risk of exaggerated radiation toxicity at the extra-cranial site, due to ongoing IPdR therapy. Since the use of palliative extra-cranial irradiation may be for a variety of extra-cranial indications, it is not feasible to account for all possible scenarios in the DLT definition. Further, for a more focused assessment of safe dose of IPdR in combination with WBRT, it is important to keep the DLT focused on neurological toxicity. Nevertheless, it will be important to monitor patients for toxicity from extra-cranial palliative radiotherapy. Hence, to note that "Any grade 3+ adverse event that might occur from palliative radiation therapy to a non-brain site concurrent or immediately post-study treatment will not be considered as DLT for the study. But such events will be recorded by the local study team and communicated to the study PI. A final decision regarding RP2D will take these events into account. Further, the local site should update the study PI (or representative) of the plan for palliative radiation, including location, dose and fractionation. No such treatment should be

started without the study PI's approval."

Any grade 3+ adverse event that might occur from SRS/SRT/fractionated boosts or neurosurgery, once the DLT assessment has been completed will be accounted for as unexpected severe late radiation toxicity and noted as secondary end-point (See 5.1 above). Use of other therapies post-DLT assessments which might impact neurological functioning (including but not limited to immunotherapy, for which safety data of immune-related neurological adverse events after WBRT is relatively limited) will be considered for this decision.

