5.1.3 Expansion Cohort

An expansion cohort of 10 additional patients will be treated at the RP2D to confirm safety and further test the exploratory biomarkers. If after 16 patients have been treated at the RP2D (6 in part 2 and 10 in the expansion cohort), there are at most 5 patients with a DLT (31.25%) then this dose will remain as the RP2D. If there are more than 5, then the next lower dose will be RP2D.

Based on the design proposed, the highest acceptable probability of DLT is 31.25% (5 or less events in 16 patients), with the target expected probability of DLT of 20-30% (of which 18-20% is expected from WBRT alone).

The following table shows some of the operating characteristics for the current design under a number of possible DLT rates. For each given dose, the table displays the likelihood of increasing to the next dose and the probability of having at most 5 patients with DLTs (out of 16). For example, if the true DLT rate is 0.4 for a given dose level, there is only a 31% chance of accruing above that dose level. If on the other hand, the true DLT rate for a given dose is 0.3 (close to target acceptable rate) and if this dose level is determined to be the MTD during the dose finding stage, then there is a 66.6% chance of having 5 or fewer patients with DLT (out of 16).

DLT Rate	Probability of dose escalation	Probability of having at most 5 Patients with DLT (out of 16)
0.1	0.906	0.997
0.2	0.709	0.918

0.3	0.494	0.660
0.4	0.309	0.329
0.5	0.172	0.105
0.6	0.082	0.019

When a patient at any site is undergoing the study treatment or is pending DLT assessment, the PI of the study (or representative) will regularly meet (in person, by teleconference or by email) with the study statistician and the participating site's study team to review any updates regarding potential adverse events being experienced by the study subject from the WBRT (or any other extracranial RT, if applicable). If necessary, clinical inputs from the treating physician and the participating site PI will be obtained to assist in the decision regarding the adverse event being labeled as a DLT.

Unexpected severe late neurologic radiation toxicity or extra-cranial radiation toxicity will be recorded as a secondary end-point. These events will be reviewed by the independent DSMB who will be charged with considering cessation of the trial if the long term/delayed (6 months) \geq grade 3 symptomatic neurotoxicity or other extra-cranial radiation toxicity is $> 20\%$.

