Use of other therapies post-DLT assessments which might impact neurological functioning (including but not limited to immunotherapy, for which safety data of immune-related neurological adverse events after WBRT is relatively limited) will be considered for this decision.

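### The late-toxicity end-point counts grade 3+ events caused by later SRS, boosts or neurosurgery without attribution to IPdR or WBRT, so the reported rate can include procedure complications

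*Combined protocol and SAP*

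**What the plan says.** Sections 3.2.3 and 5.1.4.2 allow further local treatment of the brain after the DLT assessment: "patients will be eligible to undergo SRS/SRT/fractionated boosts or neurosurgery, once the DLT assessment has been completed, if felt clinically necessary". The study calendar in section 10 puts that assessment on Day 35 or within three days after it.

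Section 5.2 then deals with the complications of such treatment. It begins "Any grade 3+ adverse event that might occur from SRS/SRT/fractionated boosts or neurosurgery" and continues "neurosurgery, once the DLT assessment has been completed will be accounted for as unexpected severe late radiation toxicity and noted as secondary end-point", with a cross-reference to 5.1.

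The end-point meant is in section 5.1.3: "Unexpected severe late neurologic radiation toxicity or extra-cranial radiation toxicity will be recorded as a secondary end-point". The next sentence there reads "These events will be reviewed by the independent DSMB who will be charged with considering cessation of the trial". The level that prompts this is more than 20% for delayed (6-month) grade 3 or worse neurotoxicity with symptoms, or extra-cranial toxicity from radiation.

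Sections 5.1.3 and 5.2 both add a qualification: "Use of other therapies post-DLT assessments which might impact neurological functioning" is to be taken into account in the decision. No rule is given for doing so. Section 13.4 contains no analysis of this end-point; its item on delayed neurological toxicity lists only HVLT-R delayed recall and FACT-BR.

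**The concern.** The sentence in 5.2 names the later procedure as the source of the event and then requires the event to be counted as radiation toxicity. For neurosurgery this is a misclassification on its face: a surgical complication is not toxicity of IPdR plus WBRT. For SRS or a boost the cause may be mixed, but nobody is asked to judge it before the event is counted.

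Late toxicity is a central safety question for a radiosensitiser given with WBRT, and a DLT window that closes around Day 35 cannot answer it. If the end-point mixes regimen toxicity with procedure complications, the published rate cannot be read as a property of the regimen. It will also vary with how often sites choose to operate or boost.

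**Working it through.** **Sections side by side**

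| Event | Where | Attribution to IPdR/WBRT needed? | How handled |
|---|---|---|---|
| DLT | 5.2 | Yes | Counted only if attributable |
| Grade 3+ event from palliative extra-cranial RT, during or just after study treatment | 5.2 | – | Not a DLT; recorded separately, reported to the study PI, weighed in the RP2D decision |
| Grade 3+ event from SRS/SRT, boost or neurosurgery after the DLT assessment | 5.2 | No | Counted in the late-toxicity end-point |
| Any adverse event | 7.2 | Graded from definite to unrelated | Recorded |

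The plan thus already collects attribution and already tracks one kind of non-study treatment event separately. The third row uses neither.

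**Which events go where**

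1. A grade 3 wound complication after a resection on Day 40 enters the end-point under 5.2. It is neither neurotoxicity nor extra-cranial radiation toxicity, and it is not delayed to six months, so it does not clearly enter the 20% count.
2. A grade 3 neurologic deficit caused by a later resection or SRS enters the end-point and could also enter the 20% count. The trigger sentence has no attribution condition.

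**Plan figure.** The 20% has no derivation, denominator or operating characteristics in the plan, so there is nothing to reproduce. The operating-characteristics table in 5.1.3 concerns DLTs and is not affected by this point.

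**Patients needed to exceed 20%.** The smallest whole number above 0.20 × n, with n an assumed denominator, is 2 of 6, 2 of 8, 3 of 10, 4 of 16, 5 of 20 and 6 of 25. Section 5.1.3 plans 16 patients at the RP2D, and 13.2 caps accrual at 25. At n = 16, one or two qualifying procedure events are 1/4 = 25% or 2/4 = 50% of the count needed.

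**Illustration on assumed rates.** The documents give none of the following:

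- b, true regimen late-toxicity rate: 5% or 10%
- f, share of patients having a later procedure: 20% to 40%
- q, grade 3+ event rate among those: 10% to 25%

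With independence, the reported rate is 1 − (1 − b)(1 − fq).

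- b = 0.10: from 1 − 0.90 × 0.98 = 0.118 to 1 − 0.90 × 0.90 = 0.190
- b = 0.05: from 1 − 0.95 × 0.98 = 0.069 to 1 − 0.95 × 0.90 = 0.145

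At n = 16 the expected number of patients with a procedure event is 16 × 0.02 = 0.32 to 16 × 0.10 = 1.6.

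For the 20% review, the exact binomial chance of crossing, **if every procedure event qualified**, is:

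| n | count needed | b | procedure events excluded | all counted |
|---|---|---|---|---|
| 10 | 3 | 0.10 | 0.070 | 0.104–0.292 |
| 16 | 4 | 0.10 | 0.068 | 0.111–0.362 |
| 16 | 4 | 0.05 | 0.007 | 0.021–0.193 |
| 25 | 6 | 0.10 | 0.033 | 0.066–0.335 |

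Under these assumed rates the last column is an upper limit, because non-neurologic procedure events may not count. If none qualified, the chance would stay at the value in the column before it.

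**The case against.** The strongest defence is that counting these events is deliberately conservative. SRS or a boost after WBRT re-irradiates brain already exposed to radiation plus a radiosensitiser, so a later necrosis may not be separable into causes, and counting everything avoids subjective discounting in a small single-arm trial. This stands for SRS and boosts, and it is why such events should not simply be excluded. It is weaker for neurosurgery.

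The DSMB also has discretion. It is asked only to consider cessation, and other therapies after the DLT assessment may be weighed. That softens the effect on the decision. It is unclear whether those other therapies include the procedures just named, and the discretion does not correct the reported end-point.

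Sections 5.4 and 5.6 end delayed-toxicity observation and take patients off study at disease progression, so events after a procedure done for progression may fall outside the window. This is arguable, because 5.5 follows patients for up to two years and the sentence in 5.2 has no such limit.

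A reader might infer three stronger things that the documents do not support:

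- **That any procedure complication, such as an early wound problem, could stop the trial.** The trigger is narrower than the end-point, and crossing it stops nothing automatically.
- **That a real signal would be hidden from the DSMB.** Attribution is graded under 7.2 and all events are reported under 7.4. With at most 25 patients, case-by-case review is feasible.
- **That few patients will be assessable at six months, so one or two events decide the matter.** The background sections cite median survivals from 2.3 to 25.30 months according to prognosis and tumour type. The assessable number is unknown.

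**Conclusion.** The concern holds for the reported end-point. As written, 5.2 puts complications of later procedures into the late-toxicity count without asking whether IPdR or WBRT contributed, and nothing elsewhere in the plan takes them out or shows them separately. The effect on the 20% review is possible but limited to events that meet its narrower definition, and it is softened by the DSMB's discretion.

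The direction is certain: adding such events can only raise the count. The size is not known from the documents. Under the assumed ranges a true 10% would be reported as 11.8% to 19.0%, and a true 5% as 6.9% to 14.5%. These figures rest on assumed procedure and event rates, on independence, and on a common denominator that the plan does not state.

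It is worth correcting because the late-toxicity result is one the trial is meant to deliver and the correction uses data already collected. It does not put the DLT rule or the RP2D decision in doubt.

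**What to change.** **Section 5.2.** Replace the sentence so that grade 3+ events following SRS/SRT, boosts or neurosurgery after the DLT assessment are recorded in a separate category, with the procedure, its date and the attribution under 7.2.

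**Section 5.1.3.** Report the late-toxicity end-point, and the percentage given to the DSMB, in two ways: (a) events with possible, probable or definite attribution to IPdR and/or WBRT; (b) all events, including those following a procedure. State the denominator for both.

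**Onset.** Count regimen-attributed events from the end of the DLT assessment. It is tempting to apply the definition of late in 5.1.4.7 (more than 90 days from treatment start), but that would leave regimen toxicity starting between about Day 36 and Day 90 in neither the DLT count nor the late end-point. The last planned fraction is on Day 26, so the two-month visit falls near Day 86, inside that gap.

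**Cost.** One sentence in each of two sections, plus a procedure and date field if not already captured. Mixed-cause events need an attribution judgement; showing both percentages lets the reader see how much depends on it. The 20% figure and permitted care do not change.

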5.3 General Concomitant Medication and Supportive Care Guidelines

Because there is a potential for interaction of IPdR with other concomitantly administered drugs, the case report form must capture the concurrent use of all other drugs, over-the-counter medications, or alternative therapies.

Permitted Supportive Therapy

All supportive therapy for optimal medical care will be given during the study period at the discretion of the attending physician(s) and documented on each site's source documents as concomitant medication. Hematologic growth factor support is acceptable. Prior/current/future hormonal therapy and/or bisphosphonates are permitted with no minimum interval to initiation of study therapy. If indicated, patients can receive palliative radiation therapy to a non-brain site concurrent or immediately post-study treatment with no minimum interval to initiation of study therapy. Any grade 3+ adverse event that might occur from this treatment will not be considered as DLT for the study.

Patients with symptoms, neurologic signs or imaging evidence of edema or mass effect should be placed on dexamethasone at the time of brain metastasis diagnosis. Steroids will be continued without taper until WBRT is completed. For this patient population, variations in the amount and frequency of steroid usage are anticipated. Per standard of care, the least amount of steroid necessary is used. Hence, it is not appropriate to define a uniform stable dose of steroid for all patients accrued to the clinical study. Patients will be used to record the use of steroid medications using the steroid medication diary in Appendix E from time of consent through the DLT assessment period.

Nevertheless, to reduce/limit any potential PK impact of the concurrent use of dexamethasone, the maximum dose of dexamethasone for the patients at the time of the start of IPdR will be restricted to 8 mg per day or lower (2 mg qid, 4 mg bid or 8 mg once a day). Patients needing more than 8 mg dexamethasone on the day of the start of IPdR will not be eligible to participate in the study. Patients already accrued in the study at a dose of 8 mg or less who subsequently need more than 8 mg of dexamethasone per day while undergoing study treatment should be reported to the study PI. This will be recorded as an AE. Steroids will be continued without taper until the whole brain radiation therapy is completed.

At the completion of WBRT, a steroid taper should be initiated provided that the patient

does not have persistent symptoms related to edema or mass effect from brain metastases. Every four days, the dose should be lowered as follows:

Table 8: Dexamethasone Taper Schedule after Completion of WBRT

8 mg Starting Dose*		Duration
2 mg four times a day	4 mg two times a day	
2 mg four times a day	4 mg two times a day	Throughout course of WBRT
2 mg two times a day	3 mg two times a day	4 days
1 mg two times a day	1 mg two times a day	4 days
1 mg once daily	1 mg once daily	4 days
1 mg every other day	1 mg every other day	4 days
Discontinue	Discontinue	

* If the daily dose is < 8 mg per day, then maintain the same dose during WBRT and thereafter reduce dose by half every 4 days until 1 mg every other day times 4 days and then stop.

In patients who cannot tolerate taper and/or cessation of steroids, the steroid dose will be maintained at the lowest dose consistent with good medical practice. Patients on steroids are recommended to receive gastritis prophylaxis and monitoring/treatment for oropharyngeal candidiasis.

Anticonvulsant usage and dosage should be noted at the time of study entry, at each follow-up evaluation and at any changes in medication use. Please refer to Section 6.4 for choice of anticonvulsant therapy.

Since, memantine use is increasingly becoming part of routine clinical practice and was considered part of the standard of care arm in the recently concluded NRG CC001 study, both twice daily memantine and extended release memantine (Namenda XR), including generic forms, will be strongly recommended. It is recommended to start memantine with the start of WBRT or the earliest feasible thereafter. The target daily dose for memantine is 20 mg (10mg divided twice daily). Dose is escalated by 5 mg per week to target of 10 mg twice daily (i.e., 5 mg a day for week 1, then 5 mg BID for week 2, then 10 mg in AM and 5 mg in PM for week 3, then 10 mg in AM and 10 mg in PM by week 4). The target dose for extended release memantine is 28 mg. Dose is escalated by 7 mg per week to target of 28 mg daily (i.e., 7 mg a day for week 1, then 14 mg a day for week 2, then 21 mg a day for week 3, then 28 mg a day for by week 4). Patients continue on memantine for 24 weeks.

At the same time, variations in practice patterns and insurance coverage for memantine exist. Variation in memantine use between patients in this phase-I study may result in potential challenges in interpreting neurocognitive evaluations. Any future phase-II study will either require either standard use of memantine (like NRG CC001 study) or stratification by its use. However, given that the primary end-point of this phase-I study is serious DLT as defined in section 5.2, to prevent any slow down in accrual, memantine use will not be mandatory.

